Potential participants will receive information in private clinic rooms for privacy. During all patient interactions, study team will do their best to ensure that no study materials/information will be left in view of others not associated with the project. The healthy volunteer arm will occur in a private laboratory.

Study outcomes during anesthesia for surgery. Follow up visits will be conducted in a private room in the clinic.
- 3 * Describe the availability of medical and/or psychological resources that subjects might need as a result of anticipated consequences of the human research:
There are always research staff available to the patient should the patient have any questions or concerns, and the Principal Investigator and/or Sub-Investigator's are likewise available to the patient.
- 4 * Describe the process to ensure that all persons assisting with the research are adequately informed about the protocol, the research procedures, and their duties and functions:
All study staff are required to go through a training process for the study with the principle investigator, which includes knowledge assessments and regular meetings to ensure that all staff are fluent in all aspects of the study.

ID: VIEW4DF83CB976400
Name: v2_Resources

Sites Where Research Activities Will Be Conducted

- 1 * Is this study a:
 Multi-Site
 Single Site
- 2 * Are you relying on an external IRB (not UM) to be the IRB of Record for this study?
 Yes No
- 3 * Are any other institutions/organizations relying on UM to be the IRB of Record for this study?
 Yes No
- 3.1 Attach the applicable regulatory documents here (i.e., IRB Authorization Agreement (IAA), FWA, local ethics approval, other IRB approvals, etc.). Final UM approval will be contingent upon final execution of all required regulatory approvals:
- | Name | Created | Modified Date |
|--|-------------------|-------------------|
| Midtown Campus IAA.pdf | 6/18/2015 4:24 PM | 6/18/2015 4:24 PM |
| University of Maryland Rehab and Ortho Institute IAA.pdf | 6/18/2015 4:23 PM | 6/18/2015 4:23 PM |
- 4 * Is UM the Coordinating Center for this study? (Applicable for multi-site studies. A Coordinating Center is responsible for overall data management, monitoring and communication among all sites, and general oversight of conduct of the project.)
 Yes No

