Aim 2: To estimate decrease in P. Acnes burden with preop skin preps compared to the contralateral side.

We hypothesize that three day preoperative application of 5% topical benzoyl peroxide will decrease patient's P. Acnes bacterial burden in comparison to chlorhexidine (positive control) and in comparison to the nonoperative shoulder (negative control).

- 2

* Discuss the research design including but not limited to such issues as: probability of group assignment, potential for subject to be randomized to placebo group, use of control subjects, etc.:

After surgical posting, patients will be randomized to chlorhexidine or benzoyl peroxide group. The solutions used will be 5% benzoyl peroxide emollient foam and 4% chlorhexidine gluconate skin cleanser. Participants will be instructed to conduct skin wash using the appropriate solution in the shower over the operative shoulder and axilla for three mornings prior to surgery (pre op day -2, pre op day -1, and morning of surgery). Specific instructions will include leaving the solution on the skin for three minutes and avoiding contact with eyes, ears, and mouth. Proper technique will be demonstrated at time of patient recruitment and given as a handout with the wash solution provided. A reminder phone call will occur two days before surgery to remind patients of proper procedure to improve compliance. On the day of surgery, patients be interviewed about pre-operative compliance.

On the day of surgery, two cultures will be taken in three separate sites on both shoulders (anterior, lateral, and posterior) using a detergent scrub technique, the current dermatologic standard for biopsy of the deep sebaceous glands. (3,11) This procedure is typically performed on the skin of awake patients and causes minimal pain and skin irritation. Cultures will be evaluated in our lab. We will also test for hemolysis as a possible indicator of a more virulent strain in the literature.

The research team may take photos of the shoulder skin being swabbed. Photos will not include the facial or defining characteristics. Photos may be taken either in the clinic at time of recruitment or in the operating room when samples are being taken.

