The patient him or herself (as opposed to a proxy) should be consented. The research staff will endeavor to answer all questions posed by the patient and his/her family to ensure their understanding of the protocol. A limited number of questions will be asked of all patients after they are introduced to the study and have reviewed the consent form. These questions assess the person's understanding of the study and what it means to participate, their appreciation of the consequences of participation, and their ability to consider alternatives to participation. The Research Coordinator will ask the questions and determine the appropriateness of the responses. If the Research Coordinator is at all unsure about the patient's ability to consent s/he will consult with the study site PI. If a patient is unable to consent, then he/she will be excluded from the study.

Recognizing that consent is an ongoing process, the study team will encourage the participants to ask additional questions that may arise during the course of their participation in the study.

The only thing different than standard treatment/surgery is the additional skin prep three days prior to surgery. Chlorhexidine scrub is standard for hip and knee replacements but we believe have limited effect on P. Acnes. Benzoyl Peroxide may treat this better. Anesthesia and antibiotic prophylaxis are standardized. Intraoperative skin prep is standardized as well. We will perform a standard dermatologic detergent scrub technique on both shoulders as a correlate of the P. Acnes burden in the sebaceous glands just prior to intraoperative skin prep. This technique is analogous to using a cotton skin swab.
- * Describe all procedures already being performed for diagnostic or treatment purposes (if not applicable to the study, enter "N/A"):**

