Potential participants will be approached by both their treating physician and the research coordinator so that any potential clinical care questions can be answered by their treating surgeon. Patients will be reminded that study participation is voluntary, and that the decision to participate or not will not alter the care they receive in any way.

Healthy members of the population will enroll strictly on a volunteer basis.

- 3 * Who will recruit participants (or acquire charts/records/samples) for this study? (Check all that apply)
PI
Study Staff

- 3.1 If you are using a third party, specify Third Party Recruiters:

- 4 Upload any recruitment tools such as screening/telephone scripts and introductory letters (do not upload advertisements here):

Name	Created	Modified Date
------	---------	---------------

There are no items to display

ID: VIEW4E0BCAA0A06C00
Name: v2_Recruitment

Advertising

- 1 * Will you be using advertisements to recruit potential participants?
 Yes No

ID: VIEW4E0BCCF811000
Name: v2_Advertising

Advertising Detail

You indicated that you will be using advertisements to recruit potential participants.

1.1 * Select the mode(s) of advertising (check all that apply):

Print

1.1.1 If Other, specify:

1.2 * Provide exact text of all proposed advertisement(s):

Shoulder infection and bacteria study.

OVERVIEW:

The shoulder infection and bacteria study is volunteer study where participants are asked to undergo a skin swab to review the level of P Acnes bacteria on skin around the shoulder. If a threshold of P Acnes is met, then participants will be randomized to try one of two antibacterial wash to assess reduction in this common bacteria. Participation is for less than two weeks and will require up to three 5-minute swab tests.

KEY ELIGIBILITY CRITERIA:

- Over 18 years of age, any gender or race

FREQUENTLY ASKED QUESTIONS:

- What is the cost of study participation to me?

Answer: None.

- Are there any risks?

Answer: There is a small risk of allergy to chlorhexidine or benzoyl peroxide

- Do I receive any compensation?

Answer: None

- Who is providing grant funding for the study?

Answer: The Orthopaedic department at the University of Maryland School of Medicine.

PARTICIPATE IN THE STUDY:

If you would like to participate in the shoulder infection and bacteria study, please contact us and leave a message at [contact]. A research team member will contact you via phone with more information.

KEY STUDY TEAM MEMBERS:

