Principal Investigator: [name], University of Maryland Orthopaedics Associates

Co-Investigator: Dr. [name], University of Maryland Orthopaedics Associates

Co-Investigator: Dr. [name], University of Maryland Orthopaedics Associates

Project Coordinators: [name] BS, University of Maryland School of Medicine and [name] BS, University of Maryland School of Medicine

1.3 * Upload advertisement(s) here:

Name	Created	Modified Date
Shoulder infection and bacteria study advertisement.docx	1/5/2017 1:40 PM	1/5/2017 1:40 PM

ID: VIEW4E0BCE82B8C00
Name: v2_Advertising Detail

Research Related Risks

If you uploaded a separate research protocol document in the 'Research Protocol' page, cite the applicable section and page numbers from that document in the answer box below.

1 * Individually list each research-related risk, using a separate line for each. Next to each risk, delineate the likelihood/seriousness of the risk, and the provisions for minimizing the risk:

There is a risk of skin reaction with any skin prep that is used in the operating room or preoperatively. Patients are screened for any allergic reaction prior to eligibility. If any skin reaction is to occur, although the risk is low, a participant should call the research team immediately to provide appropriate dermatologic care. Avoid prolonged exposure of treated areas to sun, sunlamps, or tanning booths as skin may be more sensitive after use of benzoyl peroxide or chlorhexidine.

Any time information is collected for a study there is a small risk of breach of confidentiality. However, this risk is not greater than the risk that already exists in clinical settings when handling medical data.

ID: VIEW4E1B52509F000
Name: v2_Research Related Risks

Potential Benefits and Alternatives

If you uploaded a separate research protocol document in the 'Research Protocol' page, cite the applicable section and page numbers from that document in the answer boxes below.

1 * Describe the potential direct benefit(s) to participants:

The benefit for patients would be the potential for a decrease in surgical site infection. Volunteers will have no potential benefit.

2 * Describe the importance of the knowledge expected to result from the study:

The knowledge from results of this study may change the standard of care in how we prepare patients for shoulder surgery.

3 * Describe how the potential risks to participants are reasonable in relationship to the potential benefits:

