 A consent has been prepared for the P. Acnes study and is uploaded. Individual sites may add material but may not delete material thought to be necessary for informed consent. Clinical sites may reformat and reword information to conform to their local requirements. The consent form will describe the purpose of the study, the procedures to be followed, and the risks and benefits of participation. Copies of the signed consent forms will be given to the patient, and this fact will be documented in the patient's record.
- Once eligibility has been confirmed, the informed consent process will be completed by the Research Coordinator and the attending surgeon. Patients will be approached about potential participation in the study as soon as is feasible following determination of eligibility.
- Participants will be approached and given the opportunity to enroll after surgery has been indicated. Patients often will have time to discuss the study with others prior to making a final decision to participate. Patients and their families will be provided with a pamphlet describing the study, the risks and benefits of participation and what will be expected of them if they choose to participate. Consent will be obtained in accordance with principles of GCP and ICH guidelines.
- All study materials will be provided in English.

The patient him or herself (as opposed to a proxy) should be consented.

The research staff will endeavor to answer all questions posed by the patient and his/her family to ensure their understanding of the protocol. A limited number of questions will be asked of all patients after they are introduced to the study and have reviewed the consent form. These questions assess the person's understanding of the study and what it means to participate, their appreciation of the consequences of participation, and their ability to consider alternatives to participation. If the Research Coordinator is at all unsure about the patient's ability to consent s/he will consult with the study site PI. No LARs will be used, if a patient cannot consent then they will be excluded from the study.

3 * Confirm that the consent process will explain the following:

- The activities involve research.
- The procedures to be performed.
- That participation is voluntary.
- The name and contact information for the investigator.

Yes No

4 * Describe who will obtain Informed Consent:

Attending surgeon and co-ordinator

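### Nothing in the plan keeps the treatment arm from the person who takes the hand-scrubbed cultures, so arm-aware collection can bias the primary comparison

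*Combined protocol and SAP*

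**What the plan says.** **Who meets the patient.** Informed Consent Process, item 2, states that "the informed consent process will be completed by the Research Coordinator and the attending surgeon". Study Procedures, item 1, places randomization after consent. In the Recruitment section, the question "Who will recruit participants (or acquire charts/records/samples) for this study" is answered with the principal investigator and study staff.

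**When the arm becomes known.** Justification, Objective, & Research Design, item 2, names the products: "The solutions used will be 5% benzoyl peroxide emollient foam and 4% chlorhexidine gluconate skin cleanser". It continues: "Proper technique will be demonstrated at time of patient recruitment and given as a handout with the wash solution provided". Additional Documents lists a separate instruction file for each product. Patients are also interviewed about compliance on the day of surgery; no role is named for that interview.

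**Who takes the outcome specimen.** The same item says "two cultures will be taken in three separate sites on both shoulders (anterior, lateral, and posterior) using a detergent scrub technique". Study Procedures, item 1, says "We will perform a standard dermatologic detergent scrub technique on both shoulders as a correlate of the P. Acnes burden", just before the intraoperative skin preparation. The first person plural points to the study team, but no role or individual is named.

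**What the specimens decide.** Sample Size and Data Analysis, item 2, bases the primary outcome on an aggregate chi-square comparison of proportions between the two arms.

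**Safeguards.** The only related one is in Prospective Samples, item 4: specimens carry a unique identifier set at enrollment. The application does not mention masking of the patient, sampler, laboratory reader or analyst.

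**The concern.** A detergent scrub is done by hand. It is reasonable to infer that the number of organisms recovered depends on how hard, how long and over what area the skin is scrubbed, and the application fixes none of these. If the sampler knows the arm, and the stated hypothesis favors benzoyl peroxide, a less thorough scrub in that arm would recover fewer organisms. The difference would then read as a treatment effect.

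This would happen at collection. A coded label, or even a fully masked laboratory, can only read what was collected. The contralateral shoulder is sampled too, but it serves the paired t-test, and the primary between-arm chi-square is not adjusted for it. The washes themselves may have to be open. The sampler's knowledge of the arm does not.

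**Working it through.** **1. The plan's own figure.** Inputs from Sample Size and Data Analysis, item 1: p1 = 0.36, p2 = 0.12, two-sided alpha 0.05, power 0.80, equal groups. With the mean proportion (0.36 + 0.12)/2 = 0.24:

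n per arm = [1.960 × √(2 × 0.24 × 0.76) + 0.842 × √(0.36 × 0.64 + 0.12 × 0.88)]² / 0.24² = 48.51

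This rounds up to 49 per arm, 98 in total, which matches the plan. It is not in dispute, and masking the sampler does not change it. It is also close to the expected yield: 160 × 3/4 = 120 surgical patients, less 20%, leaves 96, or 48 per arm.

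**2. Scenarios for unequal collection.** Assumptions: no true difference, 36% truly positive in both arms, 49 per arm. Collection in the benzoyl peroxide arm recovers a fraction r of the positive *patients* relative to chlorhexidine, so the observed rate there is 0.36 × r. The rejection probability is an exact sum over two independent binomials, using the Pearson chi-square test at 0.05.

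| r | Observed rates | Rejects in either direction | Rejects in favor of benzoyl peroxide |
|---|---|---|---|
| 1.00 | 36.0% vs 36.0% | 4.8% | 2.4% |
| 0.95 | 36.0% vs 34.2% | 5.2% | 3.7% |
| 0.90 | 36.0% vs 32.4% | 6.4% | 5.4% |
| 0.80 | 36.0% vs 28.8% | 11.5% | 11.2% |
| 0.70 | 36.0% vs 25.2% | 20.9% | 20.8% |

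A loss of 5% to 10% of positives changes little. A loss of 20% more than doubles the false-positive rate. The documents give no value for r, so this is a range and not an estimate.

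**3. Effect of replicate cultures.** Two cultures at three sites make six per shoulder. The plan does not say how they are combined. Suppose a patient counts as positive if any of six independent cultures is positive, and each culture in a carrier is positive with probability q. Detection is then 1 − (1 − q)⁶. If poorer scrubbing lowers q by 20%:

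- q from 0.5 to 0.4: detection falls from 0.984 to 0.953, a relative loss of about 3%.
- q from 0.2 to 0.16: detection falls from 0.738 to 0.649, a relative loss of about 12%.

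At q = 0.5, a 20% loss of positive patients needs detection of 0.8 × 0.984 = 0.7875, so q = 1 − 0.2125^(1/6) = 0.2275. That is a per-culture loss of about 55%. Under this rule replication absorbs much of a moderate change in technique. Under a rule that needs several positive cultures it may not.

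**The case against.** The strongest reply is that the overlap of people is inferred. The consent sentence shows only who takes consent, and consent comes before allocation. The sentences on demonstration, interview and culture are passive, and a first person plural identifies a team, not a person. This stands. A reader might infer that the coordinator or surgeon who enrolled a patient also scrubs that patient, or that the sampler conducts the compliance interview. The documents say neither. What they do show is that the arm is openly revealed at recruitment, that the study team samples, and that nothing separates the two tasks.

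Second, one might be tempted to say that even a slightly weaker scrub would distort the result. The figures do not support that: a 10% relative loss of positive patients adds 1.6 percentage points, and six cultures per shoulder may dilute technique effects further.

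Third, the plan calls the scrub a standard dermatologic technique. That is some standardization, but no area, duration or number of strokes is written down.

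Fourth, sampling under anesthesia might seem to stop the patient from disclosing the arm. The support for this is an incomplete sentence, "Study outcomes during anesthesia for surgery". It does not cover staff who already know the arm, or the healthy volunteers, for whom no anesthesia is described.

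Finally, the consent forms and wash handouts are listed as attachments and are not reproduced in the text. The absence of masking is therefore a statement about the application as written.

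**Conclusion.** The concern holds as an unguarded opportunity for bias in the primary comparison. The arm is openly known to recruiting staff, the study team collects the outcome specimen by hand, and no provision keeps the arm from the sampler. The documents do not establish that bias occurs, that the same individual recruits and samples, or how large any difference in recovery would be.

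If it were large enough to lose 20% to 30% of positive patients in one arm, the nominal 5% test would reject in about 11.5% to 21% of trials with no true difference. At 10% the effect is small. These figures rest on 36% truly positive in both arms, 49 per arm and loss counted per patient; the undefined rule for combining six cultures could reduce them. The change is worth making because it is cheap and no later step can repair the specimen. Confidence in the size of the effect is low.

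**What to change.** In Justification, Objective, & Research Design, item 2, and Study Procedures, item 1, state that:

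- the cultures are taken by an existing study-team or operating-room member who did not recruit, train or interview that patient and has not been told the arm;
- the scrub follows a fixed written technique, with the same area, duration and number of strokes in both arms;
- the allocation is kept off papers in the room;
- the same rule covers the healthy-volunteer retests, and volunteers are asked not to name their wash;
- where the separation cannot be kept, it is recorded that the sampler knew the arm.

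Existing staff may suffice. The advertisement lists "Project Coordinators: [name] BS, University of Maryland School of Medicine and [name] BS", so one coordinator could recruit and demonstrate while the other samples. Their availability on surgery days at both sites is not documented. The cost is a few protocol sentences and a minor rota constraint on sampling days. It needs no extra visit, procedure or participant, and the sample size is unchanged.
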